Adverse events (AEs), vital signs, physical examinations, laboratory tests, Eastern Cooperative Oncology Group (ECOG) performance status (see Appendix 1), 12-lead electrocardiogram (ECG), echocardiography, etc. during the study period; Incidence of dose-limiting toxicities (DLTs).

Secondary Endpoints:

Pharmacokinetics (PK)

Including but not limited to area under the curve (AUC_{0-t}), peak concentration (C_{max}), AUC_{0-∞}, time to peak concentration (T_{max}), apparent volume of distribution (V_d), elimination rate constant (K_e), half-life (t_{1/2}), apparent clearance (CL), mean residence time (MRT), Vd/bioavailability (F), CL/F, accumulation ratio, etc.

Efficacy

Evaluation of anti-tumor efficacy of the injected lesions based on the revised Response Evaluation Criteria in Solid Tumors version 1.1 (revised RECIST v1.1) (see Appendix 2), including objective response rate (ORR) and disease control rate (DCR); Evaluation of overall anti-tumor efficacy based on the Response Evaluation Criteria in Solid Tumors version 1.1 (RECIST v1.1) (see Appendix 3).

Note: The primary efficacy endpoints are ORR and DCR of the injected lesions based on the revised RECIST v1.1.

Exploratory Endpoints

Exploration of the levels of hydrogen peroxide (H_2O_2), peroxidase (POD), malondialdehyde (MDA), glutathione (GSH), glutathione peroxidase 4 (GPX4), hydroxyl radical ($\cdot OH$), etc. in tumor tissue samples after administration (optional);

Exploration of the intratumoral PK study in the injected lesions, if available (not mandatory);

Exploration of the dose-response relationship between tumor size and administered dose/concentration using three-dimensional reconstruction technology (3D-CTA) to guide rational dosing in future clinical trials (not mandatory).

Total number of subjects: up to 30 cases, the final sample size will depend on the number of dose groups evaluated and the tolerability in each dose group.

Number of study centers: expected to be 3-6 centers.

Subject Selection Criteria

Inclusion Criteria:

Patients must meet all of the following criteria to be eligible for enrollment:

Understand and voluntarily sign the written informed consent form (ICF), have the willingness and ability to comply with all trial requirements;

Signed the ICF and are male or female aged 18-80 years (inclusive) at the time of signing the ICF;

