Study Design: This is an open-label, dose-escalation Phase I clinical study conducted in patients with advanced solid tumors, aiming to evaluate the safety, tolerability, PK/PD characteristics, and preliminary efficacy of CNSI-Fe intratumoral injection in patients with advanced solid tumors.

Study Period: The study includes a screening period, a treatment period (including DLT evaluation period), and a follow-up period.

Screening Period: -28 to -1 days, to confirm that the subjects meet the inclusion criteria and do not meet the exclusion criteria.

Treatment Period (including DLT Evaluation Period): The DLT evaluation period is the first treatment cycle (duration: 21 days). During the DLT evaluation period, all subjects will receive CNSI-Fe intratumoral injection according to the protocol plan (preferentially selecting 1 suitable lesion for injection, tentatively with 1 injection on Day 1; if the corresponding dose of the investigational drug cannot be completed in 1 lesion, other lesions can be injected simultaneously; the dosing regimen may be adjusted by the sponsor and investigator based on the PK characteristics of this study). Safety assessments will be performed on Day 7, Day 14, and Day 21 after the first dose to evaluate DLT.

After the DLT evaluation is completed, subjects who do not experience unacceptable toxicity, if the investigator judges that the benefit of continued treatment outweighs

the risk, will enter the maintenance treatment period. In the maintenance treatment period, subjects will continue to receive one more dose of the investigational drug according to the DLT evaluation period dosing regimen (injection into the same lesion as the DLT evaluation period, tentatively with 1 injection on Day 1, the dosing regimen may be adjusted by the sponsor and investigator based on the PK characteristics of this study), and safety assessments will be performed on Day 7, Day 14, and Day 21 after dosing. Samples will be collected at the predetermined timepoints according to the study flow chart.

Follow-up Period: Safety follow-up until 28 days after the last dose.

Dose Escalation

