The DLT (Dose-Limiting Toxicity) evaluation period is in the first cycle, i.e., within 21 days after the first dose. This stage is tentatively set with 3 dose groups (calculated as Fe^{2+} , 30 mg, 60 mg, 90 mg). If ≥ 2 subjects in the 90 mg group observe DLT, the dose will be reduced to 75 mg for safety and tolerability observation; if the dose is increased to 90 mg and MTD (Maximum Tolerated Dose) is still not reached, the SRC

(Safety Review Committee) will discuss continuing to escalate the dose to 120 mg, 150 mg, or even higher (if MTD is still not reached at 120 mg, the SRC will discuss whether to stop dose escalation or directly proceed to 150 mg or even higher doses).

After 3-6 subjects in each dose group have completed the DLT evaluation, the SRC will evaluate the overall safety of each dose group based on the data obtained and determine whether to continue escalating to the next dose group or to determine the recommended dose for subsequent clinical development.

Enrollment Interval: To fully protect the safety of the subjects, during the dose escalation process, the first subject in each dose group must be dosed at least 3 days after the first dose, and the remaining subjects in that dose group can then start the first dose. The interval for subsequent subjects in the same dose group can be controlled at the discretion of the investigator. The last subject in each dose group must complete the DLT evaluation, and the safety and tolerability must be reviewed by the SRC before the first subject in the next dose group can receive the first dose.

Subject Replacement: During the DLT evaluation period, if a subject is unable to be evaluated for DLT (e.g., the subject's dose of the study drug did not reach at least 80% of the protocol-specified dose, or the subject discontinued study treatment before completing the DLT evaluation period for reasons other than DLT), additional subjects will need to be enrolled to make up the corresponding number in that dose

group.

DLT Definition: This study will grade toxicities according to NCI CTCAE v5.0. DLT refers to the following toxicity reactions that are considered by the investigator and/or the sponsor to be definitely or possibly related to the study drug CNSI-Fe, occurring within the first cycle (i.e., within 21 days after the first dose):

Hematological toxicity:

- (1) Any grade 4 hematological toxicity;

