Before the first CNSI-Fe dose, within 21 days after the first CNSI-Fe dose (specific time points to be determined based on clinical practice).

Subject to the subject's willingness, try to collect tumor tissue samples from the injected lesion before and after the first CNSI-Fe dose; the pre-dose tumor tissue sample can be the most recent archived sample or the sample collected during the screening period; post-dose tumor tissue samples will be collected according to clinical practice as much as possible to complete the tumor PK study (not a mandatory requirement).

Statistical Analysis: Analysis of the Data Set

Full Analysis Set (FAS)

The FAS includes all enrolled subjects who received at least one dose of the study drug and had a measurable lesion at baseline.

Dose-Limiting Toxicity (DLT) Analysis Set (DLTS)

The DLTS includes subjects who completed the DLT evaluation period as per the protocol (defined as receiving at least one dose of the study drug at $\geq 80\%$ of the protocol-specified dose and did not prematurely discontinue or experience a DLT during the DLT evaluation period).

Safety Analysis Set (SS)

The SS includes all subjects who received at least one dose of the study drug and had at least one post-dose safety assessment.

Pharmacokinetic (PK) Analysis Set (PKS)

The PKS includes all subjects who received at least one dose of the study drug and had at least one valid PK measurement.

Pharmacodynamic (PD) Analysis Set (PDS)

The PDS includes all subjects who received at least one dose of the study drug and had at least one valid PD endpoint measurement.

Statistical Analysis Methods

The Statistical Analysis Plan (SAP) will provide detailed specifications and descriptions of all planned statistical analyses in accordance with the protocol, and will be finalized prior to database lock.

The statistical analyses will include demographic and baseline characteristics, safety and tolerability, PK, PD, and efficacy.

The analyses will be primarily descriptive, without formal statistical hypothesis testing.

The statistical analyses will be performed using SAS® version 9.4 or higher.

The following descriptive statistical analyses will be conducted based on the nature of the variables:

Continuous variables: number of non-missing observations, mean and standard deviation (SD), median, minimum, and maximum.

Categorical variables: frequency and percentage.

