Safety Analysis: For the primary estimand, the number of subjects, incidence, and number of events of each type of adverse event will be summarized by dose group.

Numerical laboratory data at each visit will be described using mean, SD, median, extremes, and changes from baseline, and categorized as normal, clinically insignificant abnormal, or clinically significant abnormal, with the incidence of clinically significant abnormalities tabulated. The same approach will be used for ECG. Vital signs will be described using mean \pm SD.

For the secondary estimand, the incidence of DLTs will be summarized by dose

group.

PK Analysis: The primary PK endpoints for CNSI-Fe intratumoral injection will include the iron ion concentration in serum. PK analyses will provide descriptive statistics of the relevant measurements and concentration-time profiles. For the first dose of CNSI-Fe, AUC, Cmax, Tmax, and other parameters may be calculated. Descriptive statistics will be provided for these parameters, and informal testing of AUC may be performed to explore the relationship with dose.

Efficacy Analysis: Based on best lesion response, ORR, DCR, and their two-sided 95% confidence intervals (Clopper-Pearson method) will be statistically described.

PD Analysis: Descriptive statistics will be provided for the PD endpoint levels before and after dosing, as well as the changes (absolute or percent) from baseline. Corresponding time course profiles will be generated. Comparisons of the PD endpoint levels and changes from baseline at each timepoint will be performed, with normality testing and using paired t-tests or Wilcoxon signed-rank tests as appropriate.

Research on time:

After this study has been reviewed and approved by the Ethics Committee (EC), it

will continue until the expected sample size is reached, based on the actual situation.

The study is expected to end 28 days after the last participant receives a maximum of two doses. For participants who still achieve CR (complete response) or PR (partial response) at the end of the study, if the investigator determines that they can still benefit from continued treatment, they can receive the study drug free of charge until disease progression, development of intolerable toxicity, the investigator determines it is no longer appropriate for the participant to continue receiving the study drug, or the sponsor terminates the study.

Table 1-1. Clinical Trial Flow Diagram

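### The dose-AUC relationship is left to an optional, unnamed informal test; a slope with an interval on delivered dose would say more, and the dose basis for CL/F and Vd/F is not stated

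*Combined protocol and SAP*

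**What the plan says.** All references are to the synopsis of the combined protocol and SAP.

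- **PK Analysis.** The commitment is to descriptive output: "Descriptive statistics will be provided for these parameters". Beyond that, "informal testing of AUC may be performed to explore the relationship with dose". No test, model, null hypothesis or criterion is given.
- **Statistical Analysis Methods.** "The analyses will be primarily descriptive, without formal statistical hypothesis testing". Continuous variables are summarised by mean, SD, median and range. Detail is deferred to a SAP due before database lock.
- **PK Analysis Set.** "The PKS includes all subjects who received at least one dose of the study drug and had at least one valid PK measurement". There is no minimum share of the planned dose.
- **Subject Replacement.** A subject is not evaluable for DLT, and is replaced, if for example "the subject's dose of the study drug did not reach at least 80% of the protocol-specified dose".
- **Treatment Period.** Other lesions may be injected at the same time "if the corresponding dose of the investigational drug cannot be completed in 1 lesion".
- **Secondary Endpoints, Pharmacokinetics.** The listed parameters include "mean residence time (MRT), Vd/bioavailability (F), CL/F, accumulation ratio".
- **Dose levels.** 30, 60 and 90 mg are planned, with 120 mg, 150 mg or more at the safety review committee's discretion. That committee is to weigh PK/PD data together with safety and preliminary efficacy.

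**The concern.** There are two linked gaps.

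First, a test is a poor tool for exploring a dose relationship in cohorts of 3 to 6. It yields a verdict and no magnitude, and non-significance can be misread as no relationship or as proportionality. The plan commits to no slope estimate that would show how much or how little is known.

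Second, the route makes incomplete delivery foreseeable, and the plan foresees it. Subjects below 80% of dose drop out of the DLT count but stay in the PK set, and those given 80% to 99% are not replaced at all. CL/F and Vd/F take dose as an input, and so does any regression on dose, yet the visible text does not say which dose.

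What is at stake is how PK data are read when the committee considers levels above 90 mg, or when the regimen is adjusted on PK grounds. The SAP need only exist by database lock, which is later than those discussions.

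**Working it through.** **Inputs from the documents.** Doses 30, 60 and 90 mg; 3 to 6 DLT-evaluable subjects per dose; at most 30 in total. The plan gives no power, precision or CV for AUC, so it has no figure of its own to reproduce here. The three planned levels give 3 × 3 = 9 to 3 × 6 = 18 subjects. Five levels (30 to 150 mg) × 6 = 30 matches the stated maximum, though reading the 30 that way is an inference.

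**Assumptions.** Log-normal AUC; between-subject CV 40% to 60% unless stated; 90% CI for the slope; two-sided 5% for any test; AUC of the administered iron proportional to delivered dose.

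**1. Precision of a power-model slope.** Model: log(AUC) = a + b·log(dose). SE(b) = σ/√Sxx, with σ = √ln(1 + CV²).
- σ is 0.385 at CV 40% and 0.555 at CV 60%.
- 3 per group: Sxx = 1.852, t(0.95; 7 df) = 1.895. Half-width = 1.895 × 0.385/1.361 = 0.54 and 1.895 × 0.555/1.361 = 0.77.
- 6 per group: Sxx = 3.704, t(0.95; 16 df) = 1.746. Half-width = 1.746 × 0.385/1.925 = 0.35 and 1.746 × 0.555/1.925 = 0.50.
- Averaged over simulated trials, with σ estimated, the half-widths are slightly smaller: about 0.5 to 0.75 and 0.34 to 0.5.

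**2. How often a test misses a real dose relation.** True slope is 1 (AUC exactly proportional). Because the plan names no test, both forms below are assumed. Simulated share of trials that are non-significant, CV 40% to 60%:

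| Assumed form of test | 3 per group | 6 per group |
|---|---|---|
| One-way ANOVA on raw AUC | 48%–74% | 4%–35% |
| Log-log slope test | 14%–43% | about 0%–10% |

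Using the order of the doses recovers much of the lost information. At 3 per group, a null result still says little under either form.

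**3. Can proportionality be shown?** Take limits for b of 1 ± ln(1.25)/ln(3) = 0.80 to 1.20 for a 3-fold dose range (an assumed 0.80–1.25 criterion, not the plan's). At CV 30% or more, the chance that the 90% CI lies within such limits is at most 1.5% in every design examined, up to five doses with 6 each. A power model does not cure this.

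**4. CL/F if nominal dose were used.** CL/F = dose/AUC. Nominal over delivered gives an error factor of 1/f.
- f = 0.80: 1/0.80 = 1.25, so 25% too high.
- f = 0.50: 1/0.50 = 2.00, so 100% too high.

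The same factor applies to Vd/F.

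**5. Slope if nominal dose were used.** One subject at 90 mg with fraction f shifts b by (log 90 − mean log dose)·ln(f)/Sxx, and log 90 − mean log dose = 0.501.
- f = 0.50, 3 per group: 0.501 × (−0.693)/1.852 = −0.19, so 1.00 becomes 0.81.
- f = 0.50, 6 per group: 0.501 × (−0.693)/3.704 = −0.09, so 1.00 becomes 0.91.
- f = 0.80: 0.94 and 0.97.

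These count the under-dosed subject within the 3 or 6. A half-dosed subject would be replaced for DLT. If that subject is an extra one at 90 mg, the deviation and Sxx become 0.451 and 2.078 (groups of 3, 3, 4) or 0.475 and 3.942 (6, 6, 7). The slope is then 1 − 0.451 × 0.693/2.078 = 0.85, or 1 − 0.475 × 0.693/3.942 = 0.92.

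**The case against.** The strongest reply is that the plan promises very little here. The test is optional and exploratory and sits beside descriptive statistics and concentration-time profiles. The plan declares no formal testing, and no rule ties escalation to the AUC result. Informal testing could itself be a regression slope. A rising trend is often detectable, especially with 6 per group. Delivered dose and geometric summaries are ordinary SAP content, the SAP is still to come, and the supplied text breaks off before its end. Allowing other lesions to be injected limits under-dosing, whose frequency is unknown. The median and range already planned cope with some skew.

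Most of this stands, and it limits the point. A reader might infer that under-dosed subjects will be analysed at nominal dose and that CL/F will therefore be wrong. The documents do not say so; they are silent on the dose basis. A reader might also infer that dose-exposure will be decided by a group ANOVA, or that proportionality will be claimed. The text names no test, describes only exploration, and never mentions proportionality.

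The reply does not supply an estimate of the slope or a stated dose basis, and deferral to database lock leaves both open while PK data are already being considered during escalation.

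**Conclusion.** The point holds as a modest, inexpensive improvement. The visible plan commits to no estimate of the dose-AUC slope, and a non-significant informal test in cohorts of 3 to 6 would be weak evidence of anything. A pooled log-log slope with a 90% CI is a better use of the same data.

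The dose-basis gap is mainly missing detail. The 25% to 100% error in CL/F and the slope shift to 0.81 or 0.91 arise only if nominal dose is used and delivery falls to the fractions shown. The precision and test figures rest on assumed CVs, since the documents give none, and the ANOVA figures on an assumed form of the unnamed test.

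**What to change.** In the PK Analysis text and the SAP, before PK data are used in escalation discussions:

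1. Replace the informal test with a descriptive power model: log AUC and log Cmax on log delivered Fe2+ dose, pooled over all cohorts, reporting the slope with a 90% CI and no significance verdict.
2. State that delivered dose is used for CL/F, Vd/F and dose-normalised AUC.
3. Add geometric mean and geometric CV for AUC and Cmax to the planned summaries.
4. Repeat the slope without subjects below 80% of the planned dose.

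The cost is a few sentences and one extra regression with its repeat. Delivered dose is already needed to apply the 80% rule. The downside is a visibly wide interval, which should be reported as a measure of imprecision and not as evidence for or against proportionality.

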This study will enroll patients with advanced solid tumors and use the traditional "3+3 method" for dose escalation. The dose escalation principle is: in any dose cohort, 3 subjects will be enrolled first. If none of the first 3 subjects experience DLT during the DLT evaluation period, the next dose cohort can be entered. If ≥ 2 of the first 3 subjects experience DLT during the DLT evaluation period, dose escalation will be stopped (for the 30 mg cohort, if 2 DLTs occur, the sponsor and investigator will jointly decide whether to reduce the dose and continue exploration). If 1 of the first 3 subjects experiences DLT during the DLT evaluation period, an additional 3 subjects will be enrolled in that dose cohort, and if ≤ 1 of the 6 subjects in that dose cohort experience DLT during the DLT evaluation period, the next dose cohort can be entered; if ≥ 2 of the 6 subjects in that dose cohort experience DLT during the DLT

evaluation period, dose escalation will be stopped. The dose prior to the dose at which $\geq 2/3$ or $\geq 2/6$ subjects experience DLT during the DLT evaluation period will be determined as the MTD (if only 3 subjects are enrolled in a cohort, an additional 3 subjects will need to be enrolled).

The “3+3” dose escalation principle

The number of subjects who experienced a dose-limiting toxicity (DLT) within a particular dose cohort	dose escalation principle
0/3	no DLT is observed in the 3 newly enrolled subjects
0/3	no DLT is observed in the 3 newly enrolled subjects
$\geq 2/3$	Dose escalation should be stopped, and that dose will be considered the Maximum Administered Dose (MAD). If the previous lower dose was only administered to 3 subjects, then 3 more subjects need to be enrolled
1/3	
If the 3 newly enrolled subjects in the dose group do not experience a DLT (Dose-Limiting Toxicity), then the study will proceed to the next dose group.
 
 ● ● If ≥ 1 of the 3 newly enrolled subjects in the dose group experience a DLT, then dose escalation will be stopped, and that dose level will be considered the MAD (Maximum Administered Dose). The previous dose level will be considered the MTD (Maximum Tolerated Dose) (if the dose group only had 3 subjects, then an additional 3 subjects will need to be enrolled).

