Note: Unless otherwise specified, all assessments, examinations, and sample collections should be performed on the same day before drug administration.

Screening Period: Routine examinations or examination results obtained at a tertiary hospital (or this hospital) within 28 days prior to the first dose (unless otherwise specified) and before signing the informed consent form (ICF) can be used for screening, and do not need to be repeated.

Treatment Period (DLT Evaluation Period): For the first intratumoral injection of CNSI-Fe, safety assessments will be performed on Day 7 (± 1 day), Day 14 (± 1 day), and Day 21 (± 1 day) after the first dose to evaluate DLT.

Maintenance Treatment Period: After the DLT evaluation is completed, subjects without unacceptable toxicity will continue to the maintenance treatment period if the investigator determines that the benefit of continued treatment outweighs the risk. During the maintenance treatment period, subjects will receive one more dose of the investigational drug (intratumoral injection to the lesion, tentatively scheduled for Day 1, the dosing regimen may be adjusted based on the PK characteristics of this study by the sponsor and investigator).

Early Termination/End of Treatment (EOT) Visit: This will be scheduled within 7 days after the decision to discontinue treatment. If the assessments required for the

EOT visit were performed within 7 days prior to the EOT visit, they do not need to be repeated.

Safety Follow-up: Subjects who have received at least one dose of the study drug will undergo a safety visit 28 days (± 3 days) after the last dose. If the assessments required for the safety visit were performed within 3 days prior to the safety visit, they do not need to be repeated.

Medical History and Treatment History: Collected during the screening period, including past medical history, medication history (concomitant treatments within 4 weeks prior to screening and currently ongoing), history of all previous tumors (including tumor stage, diagnosis date, genetic test results), history of all previous anti-tumor treatments, family history, surgical history, immunization history, allergy history, smoking history, alcohol history, history of drug abuse/dependence, etc.

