Vital Signs: Including respiratory rate, pulse/heart rate, blood pressure, and body temperature. Measured during screening, within 2 hours before CNSI-Fe administration, 1.5 hours (± 30 minutes) after administration, on Days 7, 14, and 21 of each cycle, at the End of Treatment (EOT) visit, and during the safety follow-up visit (excluding telephone visits).

Physical Examination: Including general condition, skin and mucosa, lymph nodes,

head, neck, chest, abdomen, spine, limbs, and nervous system. A complete physical examination will be performed during screening, before CNSI-Fe administration, at the EOT visit, and during the safety follow-up visit (excluding telephone visits). Symptom-directed physical examinations will be performed during the treatment period as clinically indicated.

Body Weight: Measured during screening and before CNSI-Fe administration.

ECOG performance status, complete blood count, urinalysis, blood chemistry, coagulation function, pregnancy test (for women of childbearing potential), and tumor marker tests should be completed within 7 days prior to the first dose of the investigational drug.

12-lead ECG: Performed during screening, within 2 hours before CNSI-Fe administration, 0.5 hours (± 5 minutes), 4 hours (± 30 minutes), 8 hours (± 30 minutes), 24 hours (± 30 minutes), 48 hours (± 30 minutes), and 72 hours (± 30 minutes) after administration, on Days 7, 14, and 21 of each cycle, at the EOT visit, and during the safety follow-up visit (excluding telephone visits). Continuous cardiac monitoring will also be performed for 8 hours after CNSI-Fe administration. Additional 12-lead ECG assessments may be added during the study to ensure subject safety, at the discretion of the investigator.

Echocardiography: Left ventricular ejection fraction (LVEF). Performed during screening, and as needed during the study period if there are clinically significant ECG abnormalities.

Concomitant Medications: All concomitant medications and treatments from the time of ICF signing until 28 days after the last dose or the start of a new anti-cancer therapy (whichever occurs first) should be recorded in the patient's medical records and reported in the electronic case report form (eCRF), including the name, reason for use, dose, route of administration, frequency, start date, and stop date.

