Adverse Events (AEs): Only serious adverse events (SAEs) related to the protocol-specified procedures should be reported before the start of study drug treatment. After the start of study treatment, all AEs should be reported, regardless of their relationship to the study drug, until 28 days after the last dose. The investigator should follow up on all AEs until the event resolves to baseline or better, is considered stable by the investigator, the subject is lost to follow-up, or the subject withdraws consent. For all SAEs related to the investigational product or study procedures, every effort should be made to follow up until a final outcome can be reported.

Blood routine: Red blood cell count (RBC), hemoglobin (Hb), hematocrit, white blood cell count (WBC) and differential count (neutrophils, eosinophils, lymphocytes, monocytes, basophils and others) and platelet count (PLT). To be performed within 7

days prior to first dose of study drug in the screening period, on Day 7, Day 14, Day 21 of each cycle, at the End of Treatment (EOT) visit, and at the safety follow-up visit (excluding telephone visits). Additional blood routine tests can be performed as needed based on the investigator's clinical judgment.

Urinalysis: Urine specific gravity, urine pH, urine glucose, urine protein, urine ketone, urine red blood cells and urine white blood cells. To be performed within 7 days prior to first dose of study drug in the screening period, on Day 7, Day 14, Day 21 of each cycle, at the EOT visit, and at the safety follow-up visit (excluding telephone visits).

Biochemistry: Glucose, blood urea nitrogen (BUN) or urea, creatinine (Cr), sodium, potassium, magnesium, chloride, calcium, phosphorus, total bilirubin (TBIL), alanine aminotransferase (ALT), aspartate aminotransferase (AST), alkaline phosphatase (ALP), lactate dehydrogenase (LDH), total protein, albumin, triglycerides, total cholesterol, amylase, lipase. To be performed within 7 days prior to first dose of study drug in the screening period, on Day 7, Day 14, Day 21 of each cycle, at the EOT visit, and at the safety follow-up visit (excluding telephone visits). Additional biochemistry tests can be performed as needed based on the investigator's clinical judgment.

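### Concomitant treatments stop being recorded when a new cancer therapy starts, but adverse events are still collected to 28 days and counted under the CNSI-Fe dose group

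*Combined protocol and SAP*

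**What the plan says.** The notes under Table 1-1 give two data streams different end points after the last dose.

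- **Concomitant Medications:** recording in the medical records and the eCRF runs from consent "until 28 days after the last dose or the start of a new anti-cancer therapy (whichever occurs first".
- **Adverse Events (AEs):** once treatment has started, "all AEs should be reported, regardless of their relationship to the study drug, until 28 days after the last dose". A change of therapy does not end this.
- **Safety Follow-up:** the note states that "Subjects who have received at least one dose of the study drug will undergo a safety visit 28 days", counted from the last dose with a tolerance of 3 days either way. The laboratory notes schedule blood tests at that visit unless it is held by telephone.

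On analysis, the synopsis (Safety Analysis) says that "the number of subjects, incidence, and number of events of each type of adverse event will be summarized by dose group", and that laboratory values are described at each visit. Neither summary is cut at a new therapy or split by relatedness. The safety set has no such cut either: "The SS includes all subjects who received at least one dose of the study drug and had at least one post-dose safety assessment".

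AEs and laboratory tests are primary endpoints. Cohorts are small: "in any dose cohort, 3 subjects will be enrolled first", with expansion to 6, and the synopsis gives "Total number of subjects: up to 30 cases".

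**The concern.** The two windows part exactly when a subject changes treatment. From that day the plan goes on collecting events but no longer collects the information needed to explain them. A cytopenia or infection under the next therapy enters the table of the CNSI-Fe dose the subject last received, and so does an abnormal blood result at the safety visit. The name of the new drug, its dates and the supportive drugs given with it need not be on file.

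A statistician working on the final data could then neither show that such an event belongs to the next treatment nor rule out CNSI-Fe. Subjects have failed standard treatment or have none available, so an early switch is plausible, though the documents give no rate. What is at stake is the all-AE and laboratory picture by dose. The Safety Review Committee is to weigh each group's overall safety, not only its DLTs, when it decides on escalation or on the dose for later development.

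**Working it through.** There is no planned figure to reproduce. The check compares the two windows and then asks what one affected subject does to a cohort rate.

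**1. Length of the unrecorded stretch.** Let t be the number of days from the last dose to the start of new therapy. AEs are collected to day 28 and treatments to day t, so the stretch is max(0, 28 − t).

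| t | Stretch (days) |
|---|---|
| 7 | 21 |
| 14 | 14 |
| 21 | 7 |
| 28 | 0 |

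**2. Which values of t the schedule allows.** The Tumor assessment note puts the first scan at weeks 3-4 and scans in maintenance every 7-8 weeks. The date of dose 2 is not fixed. I assume day 22, just after the 21-day DLT period, so AE collection ends on day 22 + 28 = 50.

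- *One dose, progression at the first scan (day 21-28), switch at once:* 28 − 21 = 7 days, down to 28 − 28 = 0.
- *Two doses, scan at day 49-56, switch at once:* 50 − 49 = 1 day, down to 0.
- *First scan after dose 2.* Entry to maintenance depends on toxicity and the investigator's judgement, not on a scan, so this can happen. With a scan on day 28 and new therapy on day 35, t = 35 − 22 = 13 and the stretch is 28 − 13 = 15 days. The safety visit (25 to 31 days after dose 2) then falls 12 to 18 days into the new therapy.
- *Early stop, for example new therapy 12 days after dose 1:* 28 − 12 = 16 days. Under Subject Replacement this subject is replaced for DLT evaluation if the stop was not for a DLT, but stays in the safety set if there was a post-dose assessment.

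A different convention for counting days moves these results by about one day.

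**3. Effect on a cohort rate.** One subject who would not otherwise have had that type of event adds 1/n:

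- n = 3: 1/3 = 33.3 points
- n = 6: 1/6 = 16.7 points
- all 30 subjects: 1/30 = 3.3 points

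**4. How often it might happen (illustration only).** Assume a share s = 10-30% start new therapy inside the window, and a chance q = 30-60% of an event on it before day 28. The probability of at least one affected subject is 1 − (1 − sq)^n, with sq from 0.03 to 0.18.

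- n = 3: 1 − 0.97³ = 9% to 1 − 0.82³ = 45%
- n = 6: 1 − 0.97⁶ = 17% to 1 − 0.82⁶ = 70%

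Neither s nor q comes from the documents, and a stretch of only a few days would lower q.

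**5. DLT summary.** A DLT must fall within 21 days of the first dose and be judged definitely or possibly related to CNSI-Fe. Subjects who stop before the period ends for reasons other than DLT are replaced. Little contamination can reach this summary.

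**The case against.** The strongest reply is that the exposure is short and partly visible. On the scheduled scans the stretch is mostly 0 to 7 days. Applying the recording rule requires someone to know when the new therapy began, and that date is what a split by onset needs. The AE wording implies a judgement of relationship to study drug, so an event may be marked unrelated. Counting all events for a fixed 28 days is a conservative and defensible choice. The study is descriptive, SAP detail is deferred to before database lock, and the text available breaks off in the Tumor assessment note without Section 8.6, so a later section may close the gap.

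Much of this stands, and it rules out three stronger readings that a reader might infer.

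- *That affected events can never be identified.* The switch date and the relatedness judgement may pick out some of them. The supportable statement is that they cannot be reliably identified or verified.
- *That a scan 3-4 weeks after dose 2, with new therapy a week later, leaves a long exposed period.* That start is 28 to 35 days after the last dose, when AE reporting has ended or is ending, so the stretch is zero. At most, safety-visit bloods would be drawn up to 3 days after the switch.
- *That DLT incidence or the MTD is undermined.* Step 5 of the working shows why not.

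Two parts of the reply do not hold. A later SAP can add a cut-off or a relatedness table, but it cannot restore drug names, doses and dates that were never collected. And a relatedness judgement does not help a planned table that ignores it; without the treatment record there is also nothing to check it against.

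**Conclusion.** The mismatch is explicit in the current text and worth correcting, although its likely effect is modest. It bears on the all-AE and laboratory summaries by dose, and only for subjects who start new cancer therapy within 28 days of their last dose. For them the unrecorded stretch is mostly 0 to 7 days on the scheduled assessments, and about two weeks if the first scan follows dose 2 or the subject stops early. The two-week figures rest on the dates assumed in the working. The number of such subjects is unknown, and the case does not depend on the illustrative range. It rests on cohorts of 3 to 6, in which one misattributed subject shifts an incidence by 17 to 33 points, and on the loss being permanent once collection has stopped. The conclusion would change if a section outside the available text requires subsequent cancer therapy to be recorded.

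**What to change.** **Collection (protocol).** In the Concomitant Medications note, delete the alternative end point tied to new cancer therapy. Concomitant medications and treatments, including the name and start date of any new anti-cancer therapy, are then recorded to 28 days after the last dose for every dosed subject. Leave AE reporting at 28 days. Both windows then end together and the unrecorded stretch is zero.

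**Analysis (SAP).** Keep the all-AE table by dose group as the complete account. Add AE and laboratory summaries split at the start of new anti-cancer therapy, and list later events alongside the therapy given.

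**Cost.** A few extra eCRF entries for subjects who switch, and one date flag in the AE and laboratory programs. No visit is added, no AE data are lost, and no rule on dosing or patient management changes. The risk is that a split display hides delayed CNSI-Fe toxicity, so events after the switch must stay visible in both the full table and the listing.
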